8 INTERVENTION DISCONTINUATION

We will prepare interim analyses to evaluate the safety of the intervention after Phase 1 and again after Phase 2. One of the tasks of the Safety Monitoring Committee (SMC) will be to review preliminary data from the study and make a recommendation RE whether or not the study should continue. The following are the reasons we propose for discontinuing the study early:

- The occurrence of a serious adverse event, possibly or definitely related to the study protocol, occurring in any participant. In this study, it would include serious psychological distress causing death, suicide attempt, or hospitalization.
- Severe adverse events, possibly or definitely related to the study protocol, occurring in 3 or more participants. In this study, this would include participants who withdrew from the study due to new psychological symptoms or who were hospitalized for mental health treatment. Given the high-stress nature of the participants jobs and lives, and given MSC involves prompting participants to become aware of and attend to their own needs, it is possible that study participation prompts mental health care that had been needed previously, but was perhaps ignored or not prioritized. Thus, severe cases will be examined carefully by the PI and SMC to determine if the cases warrant study discontinuation.
- Interim analyses will provide summary data related to the above bullets and study staff will make these data available to the SMC at least 2 weeks before meeting, or within 24 hours

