7.2 Adverse Events and Serious Adverse Events

Adverse event (AE): Any unfavorable and unintended change in physical or mental health status (i.e. new or worsening physical or mental health signs, symptoms, or disease) or loss of employment associated with participation in the study, regardless of whether it is considered related to the study.

A serious adverse event (SAE): Any AE that: results in death; is life threatening, or places the participant at immediate risk of death from the event as it occurred; requires or prolongs hospitalization; causes persistent or significant disability or incapacity; results in congenital anomalies or birth defects

Unanticipated problems (UPs): Involves risks to subjects or others to include, in general, any incident, experience, or outcome that meets all of the following criteria:

- Unexpected in terms of nature, severity, or frequency given (a) the research procedures that are described in the protocol-related documents, such as the IRB-approved research protocol and informed consent document; and (b) the characteristics of the subject population being studied;
- Related or possibly related to participation in the research (“possibly related” means there is a reasonable possibility that the incident, experience, or outcome may have been caused by the procedures involved in the research); and
- Suggests that the research places subjects or others at a greater risk of harm (including physical, psychological, economic, or social harm) than was previously known or recognized.

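### Section 8 gives a related mental-health hospitalisation two discontinuation counts, one participant and three participants, and does not say whether the case review applies to a first or second admission

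*Protocol*

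**What the plan says.** Protocol section 8 (Intervention Discontinuation) asks the SMC to review preliminary data and recommend whether the study should continue. It then proposes reasons for stopping early. Two of its bullets set a count of participants.

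- **First bullet, count of one:** "The occurrence of a serious adverse event, possibly or definitely related to the study protocol, occurring in any participant". Its example is: "In this study, it would include serious psychological distress causing death, suicide attempt, or hospitalization".
- **Second bullet, count of three:** "Severe adverse events, possibly or definitely related to the study protocol, occurring in 3 or more participants". On what belongs here, it says: "this would include participants who withdrew from the study due to new psychological symptoms or who were hospitalized for mental health treatment".

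The second bullet goes on to explain that taking part may prompt participants to seek mental health care they already needed. It concludes: "Thus, severe cases will be examined carefully by the PI and SMC to determine if the cases warrant study discontinuation". The first bullet has no such sentence.

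Protocol section 7.2 defines a serious adverse event by outcome. One qualifying outcome is that the event "requires or prolongs hospitalization".

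**The concern.** A related admission for psychological or mental-health reasons is a named example under both bullets, with the same relatedness condition but different counts. The first bullet makes one such admission a reason to discontinue. The second lists the same kind of event among those that matter once three participants are affected, and it adds an argument for weighing such cases individually.

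At stake is how the SMC and the principal investigator treat a first or second related admission. One bullet says a proposed reason for stopping has been met. The other suggests the event is counted towards three and reviewed case by case. Protocol section 7 names emotional and psychological distress as a risk of the programme, and section 7.3 has depressive symptoms monitored weekly, so the protocol itself foresees events of this kind.

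**Working it through.** The documents give no operating characteristics for these reasons, so there is no figure to reproduce. The main check compares the text.

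**Step 1. Which events appear where (protocol section 8).**

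| Event, possibly or definitely related | First bullet (1 participant) | Second bullet (3 or more) |
|---|---|---|
| Death from psychological distress | named | not named |
| Suicide attempt | named | not named |
| Hospitalisation for psychological or mental-health reasons | named | named |
| Withdrawal for new psychological symptoms | not named | named |

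Only hospitalisation is named in both.

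**Step 2. Can the words serious and severe separate the two?** Serious is defined in section 7.2, and hospitalisation is one of its criteria. Severe is defined only by the second bullet's examples, one of which is hospitalisation. An adverse event that qualifies as severe through an admission is therefore also serious.

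**Step 3. Can the type of admission separate them?** Distress that leads to admission might be distinguished from an admission for overdue treatment that the course prompted. Section 8 states no criterion for that distinction. The second bullet treats its admissions as adverse events that are possibly or definitely related. Under section 7.2 they are then related serious adverse events, which the general wording of the first bullet covers.

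**Step 4. Consequence.** Every related admission counted under the second bullet has already met the first at one participant. For admissions alone, the count of three has no separate effect. Whether the case review in the second bullet governs that first admission is not stated.

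**Step 5. How far apart the two counts are (illustration only).** Planned enrolment is 15 in Aim 1 plus 30 in Aim 2, so n = 45 (protocol section 3). The documents give no admission risk p, so values of 1%, 2% and 5% are assumed. With independent participants and X the number with a related admission:

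- P(X ≥ 1) = 1 − (1 − p)^45
- P(X ≥ 3) = 1 − (1 − p)^45 − 45·p·(1 − p)^44 − 990·p²·(1 − p)^43, where 990 = 45 × 44 / 2

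At p = 0.02: P(X ≥ 1) = 1 − 0.98^45 = 0.597. P(X ≥ 3) = 0.061.

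| Assumed risk | At least 1 admission | At least 3 admissions |
|---|---|---|
| 1% | 36% | 1% |
| 2% | 60% | 6% |
| 5% | 90% | 39% |

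These are probabilities for counts of admissions. They are not the probabilities that either full criterion is met. The first bullet also covers deaths, suicide attempts and any other related serious event, and the second also counts withdrawals.

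**The case against.** The strongest reply is that the bullets are alternatives. Meeting either is enough, so one related admission is a listed reason, and the overlap is mere redundancy. Nothing in the second bullet says that fewer than three admissions is not a reason to stop. The reasons are also only proposed: the SMC makes a recommendation, so nothing stops automatically. If the SMC reviewed a first admission and advised continuing, that participant could still count towards three, together with later admissions or withdrawals.

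Reporting does not depend on the bullet either. Section 7.4 sends any related or possibly related serious adverse event to the SMC chair, the IRB and the NIA within 24 hours, and provides for ad hoc SMC meetings at the principal investigator's request.

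Most of this stands, and it limits the consequence. A reader might infer that no threshold exists for this event, or that the SMC could not tell whether a reason had been met. The documents do not support that: read as alternatives, the first bullet is met at one related admission. A reader might also infer that such an admission is the serious event most to be expected here, but the documents give no frequency or ranking of serious events.

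The reply does not remove the conflict. On the either/or reading, the count of three adds nothing of its own for admissions. The second bullet's argument for weighing such cases then sits beside a first bullet that does not mention weighing.

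Parts of the protocol (sections 4.1 and 5.1) are written as if conduct has finished. If so, a clarification can no longer guide a decision in this trial and would serve the randomised trial planned to follow. No estimate or test in the SAP is affected.

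**Conclusion.** The inconsistency is real and narrow. One event the protocol anticipates, a related admission for psychological or mental-health reasons, carries two counts, one and three, and the reach of the case review is not stated. Withdrawal for new psychological symptoms, death and suicide attempt are unaffected, because each is named under only one bullet.

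The finding rests on the wording of sections 7.2 and 8 alone. The binomial figures rest on assumed risks and independence between participants, and show only that the choice of count matters: at 1% to 5% risk, at least one admission has probability 36% to 90%, and at least three has probability 1% to 39%. The SMC's advisory role and the 24-hour reporting keep the practical effect moderate.

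**What to change.** Reconcile the first two bullets of section 8 with the serious adverse event definition in section 7.2, so that a related hospitalisation for psychological or mental-health reasons has one stated count. State whether the case review by the principal investigator and the SMC applies to that event. If two kinds of admission are meant to be treated differently, give the criterion that separates them. Which count applies is for the sponsor and the SMC to decide.

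The cost is a short protocol clarification agreed with the SMC, with no change to sample size, data collection or analysis. If conduct has ended, carry the reconciled wording into the protocol of the planned randomised trial.

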9 DATA COLLECTION AND QUALITY ASSURANCE

9.1 Data Collection Forms

ID# Convention:

All data will be de-identified with by using an ID# rather than names or other identifying information. This ID# will be composed of three numbers. The first number will be the Nursing Home with which

the participant is associated. The following ID#s numbers will be filled out by study staff after collecting completed Screening Questionnaires, starting with 01 and ending with 99.

ID#	Nursing Home
1	Aim 1 NH
2	Aim 2 NH
3	Aim 2 NH

A sample ID# will be as follows:

First Digit: NH	Second and Third Digit: Participant
1-3	01-99

Screening Questionnaire:

Initial data collection will begin with the Screening Questionnaire.

The Screening Questionnaire will be collected during information sessions by the research assistant. While presenting on the course during the information session, study staff will have an interest sheet, pre-printed with ID#s, as well as Screening Questionnaires, pre-printed with ID#s. For CNAs interested in signing into the interest sheet and participating in the Screening Questionnaire, they will sign up to a specific ID# slot, and given the corresponding Screening Questionnaire. The first page of each questionnaire will have an embedded consent form. Those present at the information sessions will be able to independently read the consent form and determine their interest in participating in the Screening Questionnaire. Any CNAs interested in participating in the full study and adding their name to the interest sheet will be told that the Screening Questionnaire must be completed in order to be eligible for the full study, but that by completing the Screening Questionnaire, they are not automatically enrolled.

While study staff is recruiting CNAs, [s]he will have a folder with them in order to collect all Questionnaires, and will instruct CNAs to bring all completed Questionnaires directly to the study staff.

Alternatively, this process will be available to CNAs over the phone if necessary (they reach out directly from flyers, are only able to stay for a few minutes at a recruitment session, but wish to complete the Screening Questionnaire at another time, etc.). In these cases, a verbal consent will be read aloud to CNAs, and the Screening Questionnaire will be read for completion.

Identifiable information from the interest sheet and linking ID#s will be transferred to an electronic folder, stored on the Cecil G. Sheps Center for Health Services Research's secure servers, separately from any data.

Baseline Interview:

This data will be collected in-person or by phone by the study staff. Study staff will bring a copy of the Baseline Interview to each in-person interview, or have a hard copy of the interview present during the telephone call. Before beginning, the study staff will write the appropriate ID# onto each interview. This ID# will have previously been assigned from the Screening Questionnaires. This interview will be done immediately after collecting consent from the participant, and will be done one-on-one, in person with the study staff. If a participant cannot complete it at the time of consenting, research staff and the participant will complete the interview at another convenient time over the phone (or in person). To aid in the data collection, study staff will provide the participant with Likert Scale cards (laminated cards with response options to various questions within the interview). This data will be collected no more than 2 weeks before the first session.

Weekly Questionnaire:

During the weekly sessions, the Weekly Questionnaire as well as the Weekly Attendance will be collected by the two study instructors.

In order to collect this questionnaire confidentially, the study instructors will have a set of manila folders – one for each participant in the program. On the manila folders, will be a Post-It note with the participants' name. Within each folder, will be a Weekly Questionnaire (with their ID# already put into their questionnaire). The instructor will hand out each folder to the study participants at the beginning of the session. Study participants will be instructed to complete the questionnaire, and put their answers back into the manila folder. At this point, the study instructor will collect all manila folders, and remove the Post-It notes with names, in order to immediately de-identify the collected data. This process will happen weekly, at each session.

For participants who need to miss a session, for whatever reason, they will be followed up with on the phone by study staff. Study staff will administer the Weekly Questionnaire – Absent Version.

For weekly sessions, study staff will meet with the intervention instructors once a week, in order to collect weekly hard copies of data from study instructors.

Semi-Structured Focus Group Guide:

The final session, a semi-structured feedback session on the Program and concepts explored in the program, includes a semi-structured focus group guide. This session will be audio-recorded.

End-of-Program Interview:

This data will be collected in phone or in person by the study staff. Research assistant will attend the final session, and bring an Sign Up for End-of-Program Interview for participants to choose when and in what form they would like to do the End-of-Program interview. Slots will be offered immediately following the session, and for immediately before and after the final semi-structured focus group. For interviews that cannot be completed at those times, study staff and participant will arrange an alternative time to either conduct a phone interview, or an in-person interview, according to the participants' convenience. Study staff will bring a copy of the End-of Program Interview to each in-person interview, or have a hard copy of the interview present during the telephone call. Once interview is confirmed (in person or phone call), study staff will arrange to either bring with them, or email or mail beforehand Likert cards (with response options for various questions in the interview) to aid in participants' responses. Before beginning, the study staff will write the appropriate ID# onto each interview. This ID# will have previously been assigned. This interview will be collected no more than two weeks after the end of the final session.

3/6 Month Follow Up Interview:

This data will be collected in phone or in person by the study staff. Study staff will bring a copy of 3/6 Month Follow Up Interview to each in-person interview, or have a hard copy of the interview present during the telephone call. Once interview is confirmed (in person or phone call), study staff will arrange to either bring with them, or email or mail beforehand Likert cards (with response options for various questions in the interview) to aid in participants' responses. Before beginning, the study staff will write the appropriate ID# onto each interview. This ID# will have previously been assigned. This data will be collected as close to the 3 month and 6 month mark post Wellbeing Program as is possible within the participants' schedules. This means data will be collected either within the two weeks before the 3/6 month mark, or within the two weeks after the 3/6 month mark.

9.2 Data Management

All data will be stored on computers and secure servers in locked offices within the Cecil G. Sheps Center for Health Services Research. All hardcopies of data will be stored in locked offices within the Sheps Center, accessible only to study staff. All hardcopies of data will be de-identified, with a linking ID# (as is the case for the Screening Questionnaire, Baseline Interview, Weekly Questionnaire, End-of-Program Interview, and 3/6 Month Follow Up Interview).

Study staff will be double entering data into Access Databases housed on the Cecil G. Sheps servers to ensure mistakes are not made during data entry. Analysis will be completed by the study staff analyst with the Program on Aging, [name].

10 PARTICIPANT RIGHTS, REIMBURSEMENT AND CONFIDENTIALITY

10.1 Institutional Review Board (IRB) Review

This protocol and the informed consent document and any subsequent modifications will be reviewed and approved by the IRB or ethics committee responsible for oversight of the study.

10.2 Informed Consent Forms

Two consenting processes are included in this study, an embedded consent for participation in the Screening Questionnaire and a written consent for participation in the study.

- A. The initial consent process is for the Screening Questionnaire of eligible participants. In the event that there are over 20 CNAs interested in a course at a single nursing home, eligible participants will be chosen from the highest scores on the Screening Questionnaire (which includes the Perceived Stress Scale). This questionnaire will be collected during information sessions by the research assistant.

While presenting on the course during the information session, study staff will have with them Screening Questionnaires with pre-printed ID#,s, as well as an embedded consent on the first page of the questionnaire. For CNAs who choose to take the Screening Questionnaire over the phone, a verbal consent will be read out to them for their response.

- B. The second consent process will be with all participants' who are committed to joining the CNA Wellbeing Program. Throughout the recruitment process, participants will be able to sign up on the interest sheet to indicate their interest. These participants will be able to sign up physically, during the recruitment sessions, or reach out directly to study staff to have their name included on the interest sheet. Once CNAs have expressed interest, the study staff will reach out to them one-on-one through their preferred method of communication (telephone, text, or email), and verify their commitment to the Wellbeing Program.

Once commitment and eligibility have been confirmed, study staff will set up one-on-one meetings with participants in order to review the written consent form. This will take place up to 2 weeks before the start date of the CNA Wellbeing Program. During this in-person meeting, study staff will review the consent form with participants and answer any questions they may have. The study staff will ensure that they have one copy of the consent form, and that the participant has another copy. Once collected, all physical consent forms will be kept in a locked office in the Cecil G. Sheps Center for Health Services Research, where only study staff will have access.

10.3 Reimbursement Schedule for Participants

Each component of the study is associated with a separate compensation (refer to Table 3), and is a nominal, non-coercive amount, to reflect the time that they will be dedicating to the study.

The CNA Wellbeing Program is being administered in two different forms of the intervention:

1. Nursing Home 1 will have the standard, MSC program (8 weeks, 2.5 hours per week) administered
2. Nursing Home 2 & 3 will have the modified, MSC program (6 weeks, 1.25 hours per week)

The original compensation of \$180 was awarded to persons in the NH #1, 8-week program, in which they were reimbursed \$25 per interview, and \$10 per class (\$25 x 4, \$10 x 8 = \$180). This equates to \$5.00 per 1.25 hours of class, and \$25.00 per interview. This reimbursement amount & schedule was changed after Nursing Home #1, after receipt of feedback from participants that the reimbursement was not commensurate to their time dedicated to the project. We also readjusted our reimbursement schedule in response to feedback – rather than waiting until the end of the intervention to reimburse participants for the first time, we added in a mid-intervention reimbursement point.

In response to feedback, the compensation per time spent in class doubled. For those in the 6-week, 1.25 hour-Program, participants will be reimbursed a total of \$140. This includes \$80 in participation in all 4 interview (\$20 each), and \$60 for their participation in 7.5 hours of intervention (\$10 per 6, 1.25 hours classes).

Table 3A – Reimbursement Payments/Schedule (for 2.5 Hour, 8-Week Program)		
Study Component	Reimbursement Amount	Schedule
Baseline Interview	\$20.00	Reimbursed once: 1. After End of Program (up to \$100)
Weekly Questionnaire	\$20/per class/questionnaire	
End-of-Program Interview	\$20.00	
3-Month Interview	\$20.00	To be reimbursed after completion of 3-Month Interview (up to \$20)
6-Month Interview	\$20.00	To be reimbursed after completion of 6-Month Interview (up to \$20)

Table 3B – Reimbursement Payments/Schedule (for 1.25 Hour, 6-Week Program)		
Study Component	Reimbursement Amount	Schedule
Baseline Interview	\$20.00	To be reimbursed twice: 1. After mid-way point (week 3) of program (up to \$50) 2. After End of Program (up to \$50)
Weekly Questionnaire	\$10/per class/questionnaire	
End-of-Program Interview	\$20.00	
3-Month Interview	\$20.00	To be reimbursed after completion of 3-Month Interview (up to \$20)
6-Month Interview	\$20.00	To be reimbursed after completion of 6-Month Interview (up to \$20)
